5.5. Procedure

Patients may be admitted the day prior to the procedure for hydration, if deemed medically necessary. Alternatively, Subjects may be admitted the day of the procedure. Antiplatelet medication should be initiated prior to placement of the study device at a dose deemed appropriate by the Investigator.

On the day of the procedure, the patient will be prepped for percutaneous intervention per institutional standards. Ultrasound-guided vascular access is recommended. When possible, a percutaneous Seldinger technique is preferred; however a cut-down may be performed when indicated. The guidewire must cross the target lesion(s) intraluminally. Use of image-centered, magnified-view contrast angiography (including a marker guidewire or catheter) is recommended.

Assessment of Lesion Characteristics

Procedural angiography will be utilized to assess target lesion characteristics and to determine final eligibility for enrollment. Lesion characteristics, including total lesion length, percent stenosis, presence of occlusion and calcification will be recorded.

Additionally, target lesion location should be recorded, confirming the presence of in-stent restenosis and noting any adjacent disease (if present).

CONFIDENTIAL INFORMATION

MD133246 Protocol Template

Revision#: 1

Doc Type: GC

Assessment of Non-covered Stent

A baseline image of the previously implanted non-covered stent prior to any study treatment is required. This image can be captured during the baseline angiogram (X-ray shot without contrast) or by plain film X-ray. Imaging will be sent to the Core Lab for assessment.

Treatment of Target Lesion and Device Deployment

Prior to study device implantation, pre-dilation of the target lesion is required with full expansion of the balloon within the lesion(s). The margins of the angioplasty treatment should be carefully marked to ensure complete coverage with the study device. The results of the pre-dilation should be evaluated angiographically. Any other pre-treatment procedures prior to balloon angioplasty may be conducted at the discretion of the Investigator.

Study device sizing, introduction, positioning and deployment should be performed in compliance with Instructions for Use (IFU). Refer to **Table 1**, GORE® VIABAHN® Endoprosthesis Configurations and Vessel Sizing Guidelines.

All areas that were pre-dilated should be covered with the study device. In addition, the study device should extend into healthy vessel a minimum of 1 cm proximal and distal to the target lesion(s). If overlapping devices is required to ensure complete coverage, there should be at least 1 cm of overlap between devices and device diameters should not differ by more than 1 mm. Post-dilation should be performed after each study device deployment to ensure seating against the vessel wall.

Procedural Completion Imaging

Final post-procedure angiogram will be performed to assess technical results. A post-procedure image is required. This image can be captured during final angiogram (X-ray shot without contrast) or by plain film X-ray. Imaging will be sent to the Core Lab for assessment.

Approved closure devices may be utilized at the Investigator's discretion. If a closure device is not used, sheath removal will be performed in accordance with institutional standard of care. Adequate hemostasis at the arterial puncture site as determined by the Investigator should be achieved prior to discharge.

Adverse events will be collected from the study procedure forward.

Discharge

Prior to discharge, a resting ABI/TBI will be measured. Discharge anti-platelet/anti-coagulation therapy and any additional adverse events will be documented.

Anti-platelet/Anti-coagulation Therapy

The Subject should be discharged and maintained on anti-platelet/anti-coagulation therapy at a dosage deemed appropriate by the Investigator.

CONFIDENTIAL INFORMATION

MD133246 Protocol Template

Revision#: 1

Doc Type: GC

The following medication regime is recommended:

- Dual anti-platelet therapy should be continued for a minimum of 6 months including Clopidogrel 75 mg PO QD (Other members of the thienopyridine class of ADP receptor inhibitors may be prescribed in place of Clopidogrel if subject intolerant to Clopidogrel) and Aspirin 81 – 325 mg PO QD
- Aspirin 81 – 325 mg PO QD should be continued through study follow-up

5.6. Repeat Interventions

In some Subjects, a repeat intervention may be required following the index procedure. Investigators should use standard of care at their institution for performing repeat interventions. An angiogram of the study lesion both pre- and post-intervention should be taken and recorded on the appropriate CRFs. All commercially available sizes of the GORE® VIABAHN® Endoprosthesis may be used for repeat interventions.

Angiography performed without subsequent intervention to maintain or re-establish patency is not considered a repeat intervention.

5.7. Follow-Up

All Subjects are required to return to the Investigator for follow-up evaluations at 30 days, 12, 24 and 36 months after the index procedure. The schedule of events is outlined in **Table 3**.

Follow-up visits will be scheduled at appointed times after the date of index procedure. The Sponsor recognizes that Subjects may not be able to return for follow-up visits on the exact date required. Thus, a period during which each visit is allowed (window) is presented in **Table 4**.

Table 4 Study Visit Windows

Follow-up Visit	Window
30 days	30 ± 7 days
12 months	365 ± 45 days
24 months	730 ± 45 days
36 months	1095 ± 45 days

The following data are required and will be collected at 30 days post-procedure:

- ABI/TBI, resting
- Rutherford Classification
- Anti-platelet/Anti-coagulant therapy assessment
- Adverse Events
- Duplex Ultrasound

The following data are required and will be collected at 12, 24 and 36 months post-procedure:

- ABI/TBI, resting
- Rutherford Classification
- Anti-platelet/Anti-coagulant therapy assessment
- Adverse Events

CONFIDENTIAL INFORMATION

MD133246 Protocol Template

Revision#: 1

Doc Type: GC

- X-ray
- Duplex Ultrasound

The following data is required and will be collected at any Unscheduled Study-Related Visit or

- ABI/TBI, resting
- Rutherford Classification
- Anti-platelet/Anti-coagulant therapy assessment
- Angiography, if indicated
- Adverse Events
- Duplex Ultrasound, if indicated

5.8. Subject Withdrawal from the Study

It is important that the Investigator encourage Subjects to return for all required follow-up visits. A Subject may withdraw from the study at any time and should notify the Investigator in this event. The Investigator may also withdraw the Subject from the study at any time based on his/her medical judgment.

If a Subject voluntarily withdraws or is withdrawn from the study for any reason, all end-of-study procedures must be performed. Any adverse events not resolved at the time of withdrawal will be classified as ongoing and the Study Completion/Discontinuation CRF will be completed. The reason for exclusion or withdrawal will be recorded and the appropriate CRFs submitted to the Sponsor.

Subjects must be withdrawn from the study for the following reasons:

- Withdrawal of informed consent (the Subject's decision to withdraw for any reason);
- Any clinical event, laboratory abnormality, or concurrent illness which, in the opinion of the Investigator, indicates that continued treatment with study therapy and participation in the study is not in the best interest of the Subject (Investigator withdrawal);
- Termination of the study by the Sponsor;
- The Subject becomes a prisoner or becomes involuntarily incarcerated for treatment of either a psychiatric or physical illness (e.g., infectious disease)

It is the right and duty of the Investigator to interrupt the treatment of any Subject whose health or well-being maybe threatened by continuation in this study or who may be experiencing unmanageable factors that may interfere with the study procedures or the interpretation of study results. Such Subjects will be withdrawn from the study rather than be allowed to continue under a modified regimen.

CONFIDENTIAL INFORMATION

MD133246 Protocol Template

Revision#: 1

Doc Type: GC

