5.10. Subject Study Completion

A Subject has completed the study when the 36 month follow-up visit has been completed. Any Subject that does not complete these requirements due to voluntary withdrawal, physician withdrawal, death, or any other reason will be considered a withdrawal. Subjects will not be provided with any medical care by the Sponsor after study completion or withdrawal. Subjects will continue to receive care per institutional standards. All Subjects, regardless of completion or withdrawal, will need a completed Study Completion/Discontinuation CRF.

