9.1.3. Adverse Event Reporting and Coding

AEs will be reported on the appropriate case report form (CRF) and documented in the Subject's permanent medical record. The Investigator at each Site is ultimately responsible for reporting AEs to the Sponsor.

The following information on each reported Adverse Event will be collected:

- Adverse Event Name
- Adverse Event Onset Date
- Relationship
- Classification Serious or Non-Serious
- Treatment
- Outcome
- Resolution Date

Adverse Events will be coded using the Medical Dictionary for Regulatory Activities (MedDRA). The Sponsor is responsible for the MedDRA classification, along with AE reporting and ongoing safety evaluation of the study in accordance with national regulatory requirements

Adverse Event submission guidelines:

- Adverse Event reporting begins once the patient is enrolled in the study following the final assessment of angiographic eligibility requirements during the study procedure. All Adverse Events should be reported from enrollment through study completion/discontinuation.
- Clinical conditions present pre-procedure are not adverse events unless the severity of the condition worsens during the course of the Subject's participation in the study.
- Provide a diagnosis if possible. If unable to provide a diagnosis, report the symptoms as separate events. Adverse Events should be reported using the full name without abbreviations or narratives.
- Adverse Events with an outcome status of "Ongoing" should be assessed at each follow-up evaluation to determine if the event has resolved. Adverse Events ongoing at study completion/discontinuation should be left as "Ongoing" on the AE case report form.

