10.1. Primary Endpoint Analysis

10.1.1. Primary Effectiveness

The primary effectiveness endpoint is Primary Patency at 12 months post-procedure. Primary patency will be estimated through 365 days along with a 95% confidence interval using Kaplan-Meier analysis. Equivalent analysis will be performed with regards to the primary patency partitioning the data by lesion length (< 230 mm and \geq 230mm). All results will be compared to that obtained in the RELINE study.

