5.4 Primary Endpoints

5.4.1 Primary Effectiveness - Primary Patency at 12 Months Post-procedure

Both the ITT and PP populations will be used with the following decision rules for calculating the primary patency at 12 Months post-procedure.

CONFIDENTIAL INFORMATION

MD133254 Statistical Analysis Plan Template
Revision#: 1
Doc Type: GC

5.4.2 Primary Safety - Procedure or Device-related Serious Adverse Events Within 30 Days of the Index Procedure

Both the ITT and PP populations will be used with the following decision rules for calculating the serious adverse events within 30 days of the index procedure.

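### Protocol 5.8 ends study observation, not only treatment, when the investigator interrupts a subject's treatment; keeping the scheduled endpoint follow-up would be a cheap improvement

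*Protocol*

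**What the plan says.** Protocol 5.8 describes investigator withdrawal twice. One bullet in the list of mandatory reasons covers clinical events, laboratory abnormalities and concurrent illness. It puts study therapy and study participation into a single judgement, so a subject cannot be off treatment but still followed. The closing paragraph then says "It is the right and duty of the Investigator to interrupt the treatment of any Subject whose health or well-being maybe threatened" by continuing, and extends this to subjects with unmanageable factors that may disturb procedures or interpretation. It ends: "Such Subjects will be withdrawn from the study rather than be allowed to continue under a modified regimen".

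The exit is not free of data. For any withdrawal, Protocol 5.8 says that "all end-of-study procedures must be performed", and the reason is recorded. Those procedures are not itemised in 5.8 or in Table 3.

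After exit the readable text stops. Protocol 5.10 says that a subject who does not complete "due to voluntary withdrawal, physician withdrawal, death, or any other reason will be considered a withdrawal" and refers the subject to institutional care. Protocol 9.1.3 says "All Adverse Events should be reported from enrollment through study completion/discontinuation".

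On the analysis side, Protocol 10.1.1 says "Primary patency will be estimated through 365 days along with a 95% confidence interval using Kaplan-Meier analysis". SAP 5.4.1 announces that both populations are used "with the following decision rules for calculating the primary patency at 12 Months post-procedure", but the rules themselves are not readable.

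**The concern.** A rule that removes a subject from the study because treatment cannot continue suits a trial of repeated dosing. Here the study treatment is a device placed at the index procedure. The visits required afterwards (Protocol 5.7) consist of assessments. The only continuing therapy that the readable protocol describes is already flexible: subjects are "maintained on anti-platelet/anti-coagulation therapy at a dosage deemed appropriate by the Investigator" (Protocol 5.5). Repeat interventions are handled within the study (Protocol 5.6). Stopping treatment therefore gives no readable reason to stop duplex, X-ray or the capture of reinterventions.

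The withdrawal grounds can relate to health, so the lost follow-up may be informative. If these subjects are censored at exit and later fail more often than the rest, Kaplan-Meier primary patency and freedom from TLR come out too high. If they fail less often, the estimates come out too low. Once observation has stopped, the study cannot tell which case applies. The same holds for the 24- and 36-month secondary endpoints.

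**Working it through.** **Does anything readable restore follow-up after an individual exit?**

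- Protocol 5.9: contact attempts are made before a subject is declared lost, not after.
- Protocol 5.10: withdrawn subjects return to institutional care.
- Protocol 5.12 and 9.1.4: explants and death documents of study subjects.
- Protocol 9.1.3: adverse-event reporting ends at discontinuation.
- Protocol 11.7: concerns the sponsor stopping the whole study, with contact only before termination.

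None provides for endpoint data after an individual leaves.

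**How large could the effect be?** The sample-size section is redacted and no expected number of withdrawals is given, so there is no plan figure to reproduce. From the documents: n = 108 and Kaplan-Meier through 365 days. Assumed: true 12-month patency S = 75%; k of 108 subjects exit (p = k/108) at a time u uniform over year 1; censoring at exit; constant hazard λ before exit and HR × λ after it, with HR from 0.5 to 6.

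Solve for λ in

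(1 - p)·exp(-λ) + p·∫₀¹ exp(-λu - HR·λ(1 - u)) du = S.

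*(a) Failures dated when they occur.* The censored Kaplan-Meier estimate tends to exp(-λ). Example, k = 3 and HR 3: λ = 0.2811, exp(-λ) = 75.49%, bias +0.49 points.

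*(b) Failures found only by the exit scan or a day-365 scan.* The estimate tends to exp(-λ)·exp(-∫₀¹ p(1 - exp(-λt))/(1 - pt) dt).

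Bias in percentage points:

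| Withdrawn | Model | HR 0.5 | HR 1 | HR 3 | HR 6 |
|---|---|---|---|---|---|
| 1 of 108 | a | -0.05 | 0 | +0.17 | +0.32 |
| 1 of 108 | b | -0.14 | -0.09 | +0.07 | +0.23 |
| 2 of 108 | a | -0.11 | 0 | +0.33 | +0.65 |
| 2 of 108 | b | -0.29 | -0.18 | +0.15 | +0.47 |
| 3 of 108 | a | -0.16 | 0 | +0.49 | +0.96 |
| 3 of 108 | b | -0.44 | -0.28 | +0.22 | +0.69 |
| 5% | a | -0.29 | 0 | +0.88 | +1.71 |
| 5% | b | -0.80 | -0.51 | +0.39 | +1.23 |
| 10% | a | -0.58 | 0 | +1.72 | +3.31 |
| 10% | b | -1.64 | -1.05 | +0.72 | +2.37 |

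HR 3 implies 12-month patency of about 57-60% among withdrawn subjects, and HR 6 about 40-45%. In model (a) at HR 3-6, one to three withdrawals give +0.2 to +1.1 points if S is 65% and +0.1 to +0.7 if S is 85%. The latter would also describe freedom from TLR at an assumed 85%.

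**Against the precision of the estimate.** Half-width = 1.96·√(0.75 × 0.25/108) = 8.2 points. The largest shift with one to three withdrawals is 0.96/8.17 = 0.12, about one eighth of it.

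**Bound that counts every exit as a failure.** This is (1 - p)·exp(-λ). Over HR 0.5 to 6:

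- k = 1, HR 6: 0.4 points below the true 75%.
- k = 3, HR 0.5: (105/108) × exp(-0.2898) = 72.8%, which is 2.2 points below.
- 5% withdrawn, HR 6: 2.1 points below.
- 10% withdrawn, HR 0.5: 8.0 points below.

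**The case against.** The strongest reply is that hardly anyone is affected. With a one-time implant and antithrombotic therapy already at the investigator's discretion, there is little treatment to interrupt, and the sentence reads like general-purpose wording. The grounds also largely concern participation itself: an investigator who judges that being in the study threatens a subject will seldom find further visits appropriate. Loss of patency, TLR and amputation are not withdrawal grounds. Exit procedures, the reason and a discontinuation form are already required, and the 30-day safety endpoint and acute procedural success are hardly touched.

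Most of this stands, and it limits the point to a minor improvement. It does not remove it. Exit procedures give status on the day of exit, not at day 365 or at 24 and 36 months. Subjects with unmanageable factors, and events that can be taken from records, remain within reach.

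A reader might infer that the rule inflates the primary result. The documents do not support that. Censoring at exit is an assumption, because the SAP decision rules and additional analyses cannot be read; the hazard ratios have no source; and the bias is zero or negative if withdrawn subjects are at equal or lower risk. In year 1, duplex is scheduled only at 30 days and 12 months, so for silent loss of patency model (b), with its smaller upward shifts, is nearer the design. Nor can one say that the SAP leaves these subjects unhandled. A censoring rule may well exist in the unreadable text, although it could not recover outcomes that were never collected.

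**Conclusion.** The point holds as a cheap, optional improvement. Protocol 5.8 ties the end of observation to the interruption of treatment without a readable reason in this design, and nothing readable collects endpoints after an individual exit. Under the stated assumptions, one to three withdrawals move 12-month patency by about -0.2 to +1.0 points (failures dated when they occur) or -0.4 to +0.7 points (failures found only by scan), against a half-width of about 8.2 points. The number of such withdrawals and the sign of the shift are both unknown. This is not a threat to the primary endpoint, and no figure in the plan is wrong.

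**What to change.** Leave the withdrawal grounds and all care decisions with the investigator, and change only what is observed afterwards.

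1. In Protocol 5.8, separate stopping study treatment or procedures from being withdrawn from the study. Reword the last sentence so that the endpoint assessments already scheduled continue where the subject still consents and the investigator judges it appropriate. Otherwise, collect reintervention, amputation and vital status from records, with consent.
2. Align the investigator-withdrawal bullet in 5.8, the classification in 5.10 and the end of adverse-event reporting in 9.1.3. A new sentence alone would conflict with all three.
3. Optionally, report the number, timing and reasons of investigator withdrawals before 12 months; the reason is already recorded. If the unreadable SAP text has no sensitivity analysis for informative exit, add one. If it counts exits as failures, label it a pessimistic bound: about 0.4-2.2 points below the true value with one to three withdrawn, and 2.1-8.0 points with 5-10%.

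The change does not reach withdrawal of consent, termination by the sponsor or, in practice, incarceration.

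Cost: an amendment with IRB/EC approval (Protocol 6.6) and possibly consent text, best bundled with the next amendment, plus a few visits already on the schedule or record checks. No new type of test is needed.

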5.9. Subject Retention Strategy and Loss to Follow-Up

Subject retention is important to the validity of study outcomes. At the time of subject enrollment and execution of the patient informed consent, the Investigator and/or designee, will discuss the importance of complying with protocol requirements and the follow-up visit schedule (Refer to Section 4.2, Clinical Inclusion Criteria #7). Individual considerations that may preclude a Subject from returning for a study follow-up visit (e.g., transportation, distance, scheduling constraints) should be identified and adequately addressed prior to enrolling a Subject into the study to mitigate future loss to follow-up. At the time of the follow-up visit, the Investigator or designee will again discuss the expectation that the Subject will comply with the protocol's follow-up schedule and address any individual concerns that would prevent continued compliance.

The study objectives may not be realized if a significant number of Subjects are lost to follow-up. A Subject will be considered lost to follow-up and withdrawn from the study once they have missed two consecutive follow-up visits and three documented attempts have been made by the Investigator or designee to contact the Subject or next of kin. One of the three documented attempts must include a certified letter.

5.10. Subject Study Completion

A Subject has completed the study when the 36 month follow-up visit has been completed. Any Subject that does not complete these requirements due to voluntary withdrawal, physician withdrawal, death, or any other reason will be considered a withdrawal. Subjects will not be provided with any medical care by the Sponsor after study completion or withdrawal. Subjects will continue to receive care per institutional standards. All Subjects, regardless of completion or withdrawal, will need a completed Study Completion/Discontinuation CRF.

5.11. Device Deficiencies

The Study Devices are commercially available in the U.S and the EU. Device deficiencies and complaints should be reported through normal product surveillance mechanisms.

5.12. Explant Procedures

The Study Device may be explanted during a surgical procedure or as part of an autopsy. Sites are requested to return explanted device to the Sponsor for gross and histological evaluation. Prior to planned or potential device retrieval, contact the Gore Associate managing the study to communicate that a specimen is being retrieved from a study Subject. A specimen shipping kit will be immediately sent to the Site. The specimen kit provides specific packaging and handling instructions for the specimen and contains a shipping container.

6. Study Administration

6.1. Training

All Investigators implanting devices in this clinical study must be trained on the protocol and Instructions for Use (IFU) by Sponsor associates, designees or another appropriately trained physician at the study Site.

CONFIDENTIAL INFORMATION

MD133246 Protocol Template

Revision#: 1

Doc Type: GC

